9.0 Vulnerable Populations

9.1 Vulnerable Populations:

Population / Group	Identify whether any of the following populations will be targeted, included (not necessarily targeted) or excluded from participation in the study.
Children	Targeted Population
Pregnant women/fetuses/neonates	Excluded from Participation
Prisoners	Excluded from Participation
Adults lacking capacity to consent and/or adults with diminished capacity to consent, including, but not limited to, those with acute medical conditions, psychiatric disorders, neurologic disorders, developmental disorders, and behavioral disorders	Excluded from Participation
Non-English speakers	Included/Allowed to Participate
Those unable to read (illiterate)	Excluded from Participation
Employees of the researcher	Excluded from Participation
Students of the researcher	Excluded from Participation
Undervalued or disenfranchised social group	Included/Allowed to Participate
Active members of the military (service members), DoD personnel (including civilian employees)	Excluded from Participation
Individual or group that is approached for participation in research during a stressful situation	Excluded from Participation

such as emergency room setting, childbirth (labor), etc.	
Individual or group that is disadvantaged in the distribution of social goods and services such as income, housing, or healthcare.	Included/Allowed to Participate
Individual or group with a serious health condition for which there are no satisfactory standard treatments.	Included/Allowed to Participate
Individual or group with a fear of negative consequences for not participating in the research (e.g. institutionalization, deportation, disclosure of stigmatizing behavior).	Included/Allowed to Participate
Any other circumstance/dynamic that could increase vulnerability to coercion or exploitation that might influence consent to research or decision to continue in research.	Included/Allowed to Participate

9.2 Additional Safeguards:

Minor children will be enrolled in this study and will be asked to sign an assent form after their parents or legal guardian(s) sign a parental consent form. Legal guardians will be asked to provide proof of their status. If a minor child turns 18 while they are participating in the project, they will be asked to sign an adult consent form and HIPAA authorization at their next scheduled visit to indicate their willingness to stay in the study.

A parental consent form in Spanish has been created as a number of our participant children may be bilingual, but their parent may not be as comfortable with speaking English.

9.2 Local Number of Participants to be Consented:

We plan to enroll 30 participants into this pilot study.

**10.0 Local Recruitment Methods**

10.1 Recruitment Process:

We will work with Fairview Research Administration to identify potential participants who have not opted out of hearing about research projects and send

them a letter. Interested participants will be asked to contact the study team and up to three follow-up phone calls will be made by study staff if no initial response is received. We will also reach out directly to the patient's primary care provider or primary diabetes provider to inform the provider that their patient is possibly eligible for this study and provide them with a flyer for the patient. The patient can then contact the research coordinator directly or give verbal permission to be contacted.

Children's Minnesota will also send out recruitment letters to their patients.

#### *10.2 Identification of Potential Participants:*

Potential participants may self-identify by calling the study coordinator after receiving a recruitment letter (described above). Additionally, [name] may approach potential participants that she sees as part of standard care who may qualify for the project and inquire about their willingness to learn more.

#### *10.3 Recruitment Materials:*

A recruitment letter will be used to recruit potential participants. A recruitment flyer with study information will be given to patients in T2D clinic.

Endocrinologists within Park Nicollet and Children's will also be provided with a flyer to provide to interested patients who are seen in their clinic and will send out recruitment letters.

#### *10.4 Payment:*

Participants will be compensated for the study items that they complete. Participants can earn a total of \$2265. The amount to be earned is broken down as follows:

- Screening visit \$75
- Baseline visit: \$100
- Week 4: \$20 for review of CGM data
- Week 8: \$20 for review of CGM data
- Week 12: \$115 (\$95 for the visit and blood draw, \$20 for CGM review)
- Week 16: \$20 for review of CGM data
- Week 20: \$20 for review of CGM data
- Week 24: \$120 (\$100 for in-person visit and \$20 for review of CGM data)
- Week 28: \$20 for review of CGM data
- Week 32: \$20 for review of CGM data
- Week 36: \$115 (\$95 for the visit and blood draw, \$20 for CGM review)
- Week 40: \$20 for review of CGM data
- Week 44: \$20 for review of CGM data
- Week 48: \$20 for review of CGM data

- Week 52: \$120 (\$100 for in-person visit and \$20 for review of CGM data)
- Swiping of the Libre CGM: \$2/swipe (participants will be asked to swipe twice per day (\$4 maximum per day, or \$120 for a full month of swiping twice per day). For participants on the Dexcom G7, the data retrieval is automatic (swiping is not required) and participants will receive \$4/day for each day the CGM is worn (maximum of \$120 for each month).

The Greenphire ClinCard will be used for all compensation.

## **11.0 Withdrawal of Participants**

### *11.1 Withdrawal Circumstances:*

Participants who ask to be withdrawn from the project will have their request honored. Participants may be asked to come to one final study visit for a physical examination and hemoglobin A1c measurement for safety, if the PI thinks that this is required, and discuss how their insulin should be adjusted after taking PHN/TPM or placebo is stopped.

Participants who are not uploading their CGM data may be withdrawn from the study at the PI's discretion.

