Glycemic Control: Time in range (BG of 70-180 mg/dL) and hypoglycemic events will be measured using Continuous Glucose Monitors, either Freestyle Libre 14 day or Dexcom G7. The Freestyle Libre 14 day is no longer being produced so we will phase in the use of Dexcom G7 CGM. Worn on the skin, the disposable, single use sensor will continually measure glucose levels from the interstitium, every minute for 14 days (Libre) or 10 days (Dexcom G7) and will upload the data for review, and the participant will be asked to share this data with the study team. Participants will be taught how to place and replace the CGM. Participants who have a Libre CGM will be instructed to swipe the sensor at least twice daily (fasting and at bedtime) and to upload their CGM data monthly. Participants who have the Dexcom CGM will not need to swipe, but will be instructed to upload their CGM data monthly. CGM data will also be used to titrate insulin and metformin dosing. Percent time of CGM use will be used to assess adherence.

Total daily insulin dose: For participants on insulin therapy, total daily insulin dose (units/kg/day) will be averaged over the previous month at each study visits. Participants will log their insulin doses and return pens to study visits.

Body composition: Total body and visceral fat (% and kg) and measures of bone mineral density will be measured by dual energy x-ray absorptiometry (iDXA). iDXA measurements, using standard positioning techniques, will be conducted and analyzed by trained staff.

Anthropometrics: Height and weight will be collected by trained research staff at weeks 0, 12, 24, 36 and 52. Weight only will be collected at Weeks 4, 8, 16, 20, 28, 32, 40, 44, and 48. Weight will be collected via a scale provided to the participants and reported directly to the research coordinator at Week 28, 32, 40, 44, and 48 if there no monthly visits and per the PI's discretion.

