### *11.2 Withdrawal Procedures:*

Participants who wish to withdraw from the study will be allowed to do so. They will also be offered to stop taking the study medication/placebo but continue with the visits.

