### *11.3 Termination Procedures:*

Participants who withdraw from the study will not have additional study information collected. Data that had been collected prior to their withdraw will still be reviewed and utilized.

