## 14.0 Statistical Considerations

### 14.1 Data Analysis Plan:

There are 3 analysis populations planned, Intention-to-treat (ITT) will include any participant randomized according to their treatment assignment. Per-protocol (PP) will include those without protocol violations and who were compliant ( $\geq 80\%$ ) with their treatment assignment measured by medication log and medication collection. The safety population will include all who receive treatment, according to treatment received.

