### 14.3 Statistical Analysis:

Descriptive analyses of baseline characteristics and outcomes will include means and standard deviations, median and range for continuous variables and frequencies for categorical variables. Treatment adherence will also be evaluated by the methods described above. Safety analyses will be primarily descriptive reporting the number and percentage of adverse events. All safety outcomes will be evaluated and monitored throughout the trial. Confidence intervals (CIs) and p-values will be based on robust variance estimation. Statistical significance will be considered as  $p < 0.05$ .

Aim 1: The primary analysis will be conducted using the ITT population to compare the mean BMI percent change (primary outcome measure) from randomization to 6 months of follow-up between the groups, adjusted for BMI at randomization for added precision. We hypothesize that with participants treated with PHN/TPM will demonstrate greater BMI percent change compared to controls at 6 months. Supportive analyses using the PP population will also be conducted along with consideration of adjustment for residual imbalances

between treatment groups after randomization (e.g., in sex as a biological variable). Longitudinal analyses will also be conducted, incorporating the multiple time points through the open-label extension (6 months to 12 months follow-up) during which these BMI measurements will be obtained. This will examine durability of changes observed over the masked portion of follow-up, as well as provide additional safety information. Supportive analyses using the PP population will also be conducted.

Aim 2: Secondary outcomes will be analyzed in the same fashion as the primary endpoint wherein analyses will be adjusted for values at randomization. Outcome measures for Aim 2 are c-peptide index ( $\Delta C_{30}/\Delta G_{30}$ ), insulin sensitivity (1/fasting insulin),  $\beta$ -cell function relative to insulin sensitivity (oral disposition index [oDI]), A1c (%), and total daily insulin dose (units/kg/day). We hypothesize that participants treated with PHN/TPM will demonstrate improved insulin sensitivity and  $\beta$ -cell function compared to those assigned to placebo as measured by OGTT, A1c and total daily insulin doses. Complementary secondary analyses will also be conducted for each secondary outcome as described for the primary outcome.

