#### 14.4 Data Integrity:

Despite efforts, it is possible that some data will be missing, which could limit the interpretation and generalizability of results. If the data are missing at random, conditioned on measured covariates, then supplementary analyses adjusting for these covariates will produce unbiased results. For potential missing data mechanisms beyond measured covariates, we will examine the extent to which results may be affected. Imputation techniques will be considered for missing data issues (e.g., multiple imputation). In particular, for the primary analysis we will use a last observation carried forward approach for participants on whom we do not have a final measurement. Additional complementary analyses will incorporate Markov Chain Monte Carlo (MCMC) multiple imputation to handle missing data. The imputation model will be stratified by treatment group and include baseline values at randomization. Additional variables for possible inclusion in the model include age, race, sex, and Tanner stage, though unlikely to be more than one in any single model due to sample size limitations. MCMC imputation will be used to estimate treatment group differences, 95% confidence intervals and P values; observed data will be used to estimate within treatment group changes. If the analyses with and without multiple imputed values differ

substantially, then exploratory analyses will be performed to evaluate factors that may have contributed to the differences. Secondary endpoints will be handled similarly.

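### Study withdrawal for not uploading CGM data can end week-24 BMI follow-up in a willing participant, leaving the primary analysis to a carried-forward value

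*Combined protocol and SAP*

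**What the plan says.** Four parts of the combined protocol and SAP bear on this point.

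- **Ground for withdrawal (11.1).** "Participants who are not uploading their CGM data may be withdrawn from the study at the PI's discretion". The removal is from the study, not only from study treatment. No threshold for non-upload is given.
- **Consequence (11.3).** "Participants who withdraw from the study will not have additional study information collected". The next sentence preserves what already exists: "Data that had been collected prior to their withdraw will still be reviewed and utilized".
- **Alternative to full withdrawal (11.2).** For people who wish to withdraw, "They will also be offered to stop taking the study medication/placebo but continue with the visits". Nothing extends this to a participant whom the investigator removes. The optional final visit in 11.1 is likewise written for those who ask to leave, and it names a physical examination and HbA1c, not height and weight.
- **Analysis (14.1, 14.3, 14.4).** "Intention-to-treat (ITT) will include any participant randomized according to their treatment assignment". "The primary analysis will be conducted using the ITT population to compare the mean BMI percent change (primary outcome measure) from randomization to 6 months". For missing final values, "for the primary analysis we will use a last observation carried forward approach for participants on whom we do not have a final measurement". Multiple imputation is a complementary analysis.

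BMI comes from clinic measurements. Section 5.2 (Anthropometrics) states: "Height and weight will be collected by trained research staff at weeks 0, 12, 24, 36 and 52". At weeks 4, 8, 16 and 20 only weight is taken.

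**The concern.** Failing to upload CGM data is not a withdrawal of consent. The participant may be quite willing to attend at week 24. Under 11.1 and 11.3 together, that person's week-24 BMI need not be collected, although it could be obtained at a visit already on the schedule.

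The outcomes listed in 14.3 do not need the upload either. BMI needs height and weight. The Aim 2 measures are OGTT indices, fasting insulin, HbA1c and total daily insulin dose, and 5.2 has participants log their insulin doses and return their pens. The exploratory measures are body fat and cardiometabolic values. Removal from the study gives up all later values of these.

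The missingness may also be informative, because 5.2 treats percent time of CGM use as an adherence measure. The complementary imputation model in 14.4 names treatment group, baseline value, age, race, sex and Tanner stage, but not upload status, so it would not condition on the reason for removal.

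With 30 participants, each avoidable missing primary outcome counts.

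**Working it through.** **1. Reproduce the stated power (14.2).** Inputs: SD 8.9, baseline to follow-up correlation 0.75, 15 per arm, type I error 0.05. Sidedness is not stated; a two-sided normal approximation matches.

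- Baseline-adjusted SD = 8.9 × √(1 − 0.75²) = 5.887.
- Standard error of the difference = 5.887 × √(2/15) = 2.150.
- Power for 6% = Φ(6/2.150 − 1.96) = Φ(0.83) = 79.7%. The plan says 80%.
- With 10% attrition (13.5 per arm), the standard error is 2.266 and power for 6.3% is 79.4%. The plan again says 80%.

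Both figures reproduce. A noncentral t calculation gives 76.9% for the first.

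**2. Who stays in the analysis.** By 14.1, all 30 randomized participants remain in the intention-to-treat set after any CGM withdrawal. By 11.3 their earlier data are used, and by 14.4 the missing week-24 value is filled by last observation carried forward (LOCF). The observed week-24 BMI is lost; set membership is not.

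**3. Which value is carried forward.** In the masked period, height and weight are scheduled together at weeks 0, 12 and 24 (5.2 and footnote a of the Schedule of Events). The last complete BMI before week 24 is therefore normally that of week 0 or week 12. A later weight could be paired with an earlier height, but the plan does not specify this.

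**4. Illustrative size.** The documents give no rate of CGM non-upload or of withdrawal for it. Assumptions:

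- a fraction w of each arm is withdrawn before week 24;
- those withdrawn would otherwise have shown the same effect as the rest;
- baseline BMI is carried forward, so their recorded change is zero;
- there is no change on placebo (with equal w in both arms this is not needed, because the placebo mean scales by the same factor);
- the adjusted SD stays at 5.887.

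Expected difference = 6 × (1 − w), with all 30 analysed:

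| w | Expected difference | Power, normal approximation | Power, noncentral t |
|---|---|---|---|
| 0 | 6.0% | 79.7% | 76.9% |
| 10% (3 of 30) | 5.4% | Φ(5.4/2.150 − 1.96) = about 71% | 67.9% |
| 20% (6 of 30) | 4.8% | Φ(4.8/2.150 − 1.96) = about 61% | 57.8% |

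**5. Direction.** Step 4 is one case among several.

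- If those withdrawn had no drug effect, the true intention-to-treat difference would itself be 5.4% or 4.8%, and carrying baseline forward would cause no error.
- If they had half the effect, the true values would be 6 × (1 − 0.5w) = 5.7% and 5.4%. The estimate would be low by 0.3/5.7 = 5% and 0.6/5.4 = 11%.
- If a week-12 loss on drug were carried forward in someone who would have regained by week 24, the estimate would be too favourable to the drug.
- If later gain on placebo were hidden, the estimate would be too small.

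**The case against.** **The rule has an evident reason.** CGM data guide insulin and metformin titration (4.1, 5.2), and hypoglycemic episodes are documented by CGM and reviewed monthly (12.1). Section 11.1 gives no rationale, but an investigator without glucose data has a real monitoring problem. It would be wrong to say that safety plays no part. This stands. It bears on treatment and glucose management, however, and does not explain why weighing and measuring should stop. Section 11.2 already separates the two for people who choose to leave.

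**The loss may be small.** The rule says that participants may be withdrawn, not that they will be. Upload help is available at the unit (8.3), the Dexcom needs no swiping (5.2), and review and wear are paid (10.4). A removal after week 24 costs the 6-month outcome nothing. Three losses in 30 equal the 10% attrition allowed for in 14.2. All of this stands, so the figures above are a range and not a forecast. The attrition allowance would nevertheless be spent partly on people willing to stay.

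**A stronger reading is tempting.** A reader might infer that the intention-to-treat set sheds its least adherent members and the drug effect is overstated. For example, if 10% to 20% with 0% to 50% of the effect were dropped, the estimate would be 6.0% against a true 4.8% to 5.7%, which is 5% to 25% too high. The documents do not support this. It describes a completers-only analysis, whereas 14.1 keeps everyone and 14.4 fills the value. Nor does any section link CGM uploading to capsule-taking, which is measured by medication log and returned product (4.1, 14.1).

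**Conclusion.** The point holds in limited form. Read together, 11.1 and 11.3 allow an obtainable week-24 BMI to be replaced by a carried-forward value in a participant who would still attend, for lack of a data stream that the primary outcome does not use. The 11.2 offer does not cover this case.

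The analysis set stays at 30. The harm is reliance on LOCF, and on an imputation model that does not name the reason for removal. On the assumptions in step 4, 10% to 20% withdrawn before week 24 would reduce a 6% difference to 5.4% to 4.8%, with power of about 71% to 61%. The rates, the timing, the value carried forward and the effect in those withdrawn are all assumed, and the sign of any bias is not determined. This is an inexpensive improvement to a small trial, not a demonstrated distortion of its primary comparison.

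**What to change.** Amend 11.1 to 11.3 in three respects.

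- **11.1:** *Failure to upload CGM data alone does not end a participant's follow-up in the study.*
- **11.2:** Extend the offer to continue visits, including week-24 height and weight, to participants whom the investigator would otherwise withdraw on this ground.
- **11.3:** State that collection ends only when the participant leaves follow-up. Any decision about study treatment or glucose management made for lack of CGM data stays with the investigator and is recorded separately from follow-up status.

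The cost is a few lines in the next amendment. The visits are already scheduled and the sample size does not change. The downside is that these participants must still be seen at those visits, and their CGM-based data will still be missing.

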### *11.2 Withdrawal Procedures:*

Participants who wish to withdraw from the study will be allowed to do so. They will also be offered to stop taking the study medication/placebo but continue with the visits.

### *11.3 Termination Procedures:*

Participants who withdraw from the study will not have additional study information collected. Data that had been collected prior to their withdraw will still be reviewed and utilized.

## **12.0 Risks to Participants**

### *12.1 Foreseeable Risks:*

#### *Expected Adverse Events*

PHN/TPM: Adverse events will be reviewed and documented at each study visit and phone call (monitored monthly throughout the study). Participants will be instructed to contact study staff immediately if any adverse event is experienced. Overall, the safety profile of PHN/TPM has been demonstrated to be acceptable in adults, with paresthesia (mild tingling in the extremities), dysgeusia (altered taste), insomnia, constipation, and dry mouth as the most commonly reported (incidence  $\geq 5\%$ ). Of note, topiramate use during the first trimester of pregnancy is associated with an increased risk of oral clefts in the fetus. A basic metabolic panel at weeks 0, 24, and 52, and urine pregnancy test (for persons of child-

bearing potential) will be performed monthly. We will require all sexually active participants who are of child-bearing potential to confirm use of at least two forms of effective contraception. In addition, we will monitor for potential changes in depression, anxiety, suicidal behavior and ideation, acute myopia and secondary angle closure glaucoma, mood and sleep disorders, cognitive impairment, metabolic acidosis, kidney stones, and elevated creatinine. Participants will be asked to increase their fluid intake in order to help decrease the concentration of substances involved in kidney formation. Topiramate can increase the risk of suicidal ideation and behavior. Participants will be screened for depression with the PHQ-9 and suicidal ideation and behavior with the C-SSRS. If any questionnaire reveals suicidal behavior or ideation with some intent to act on it, then test results will be confirmed by the PI prior to discharging the subject from the study. Study medications will be weaned off if there is suicidal behavior or ideation with some intent to act on it.

**Insulin:** Participants may already be on insulin therapy upon enrollment in the study or it may be used to treat hyperglycemia. There is a risk of bruising, bleeding and infection associated with insulin injection. Hypoglycemia may also occur with insulin use, and this risk increases with weight loss. Participants who are on insulin will be trained on the signs of low blood sugar and how to treat an episode of hypoglycemia. Hypoglycemic episodes will be documented by CGM and reviewed monthly, or sooner if needed. Doses of metformin and insulin (if applicable) will be down titrated to help prevent further hypoglycemia.

**Metformin:** Participants may already be on metformin therapy upon enrollment into the study or the metformin dose may be titrated during the course of the study. Side effects of metformin include diarrhea, bloating, nausea and vomiting, which are usually self-resolving. Side effects will be reviewed at each study visit and metformin can be down titrated or discontinued if warranted by the PI. Participants can be on either immediate-release or extended-release formulations of metformin.

**OGTT:** There is a minimal risk of bruising, bleeding and infection associated with the blood draw and peripheral IV placement for the OGTT. There is also a risk of temporary hyperglycemia during the testing.

**Continuous Glucose Monitoring:** There is a minimal risk of bruising, bleeding, and infection associated with placement of the CGM device. Participants will be trained how to apply the device at baseline. In general, CGM is well tolerated and accepted. A diabetes clinical nurse will be available to participants to help address any issues with CGM placement and maintenance remotely.

**Screening and monitoring labs:** The risks of drawing blood for this test include bruising, bleeding and infection at the site where the needle enters the skin. On rare occasions, fainting may occur.

Dual Energy X-ray Absorptiometry (iDXA): The iDXA scans involve exposure to a very low dose of ionizing radiation to generate their picture. The average amount of radiation that the average person would receive from the iDXA scans in this study is less than 1% (3 mrem) of that received from natural sources of radiation by a Minnesota resident in one year (300 mrem).

Risks of Questionnaires, EDE-Q, PHQ-9, C-SSRS, PedsQL: Individuals may feel self-conscious or nervous about answering these questions. However, the risk of being able to provide an intervention if an individual develops unhealthy eating habits or suicidal ideations is felt to outweigh the risks.

There is always a risk of a breach in confidentiality associated with the use of data that can be linked back to individuals. The study team will utilize password protected programs in which to enter data and study data in paper form will be kept in offices that are locked when unattended.

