Patient Health Questionnaire-9 (PHQ-9): The PHQ-9 measures depression and suicidality. The PHQ-9 Modified for Teens will be administered to participants < 18 years of age. A participant will be referred to a mental health professional or primary care provider if s/he has a PHQ-9 score of  $\geq 10$  or reports any suicidal behavior. A PHQ-9 score  $\geq 15$  at the screening vision is an exclusion criteria.

Columbia-Suicide Severity Rating Scale (C-SSRS): The C-SSRS measures depression and suicidality. A participant will be referred to a mental health professional or primary care provider if s/he has any suicidal behavior or any suicidal ideation of type 4 or 5 on the C-SSRS. Please see Exclusion Criteria for cut-off scores related to the C-SSRS.

Pediatric Quality of Life Inventory (PedsQL™): The PedsQL measures general and disease-specific quality of life. We will be using the participant-reported measures for the PedsQL™ Generic Core Scales and Diabetes Module Version 3.2 for young adults (aged 18-25 years) and Teens (12-18 years).

Oral Glucose Tolerance Test (OGTT): Insulin sensitivity and  $\beta$ -cell function will be measured via a 2-hour, 75 mg oral glucose tolerance test. OGTT has been widely used in the evaluation of  $\beta$ -cell dysfunction and T2D, including in the TODAY and RISE studies. The OGTT will be performed following a 10-12 hour overnight fast. Participants will take their last dose of metformin (if applicable) the evening before testing. Participants on basal or bolus insulin will be asked to withhold insulin dose either 36 hours or 6 hours, respectively, prior to testing. Plasma glucose levels, C-peptide, and insulin levels will be measured at baseline, 30, 60, 90 and 120 minutes following standard glucose ingestion. If a participant comes to a visit and has not withheld insulin for the required number of hours, the visit

will proceed without the OGTT and the participant will be asked to return to perform the OGTT within one week of the originally scheduled visit.

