**Participant Safety:** At the outset, participant risk will be minimized by study team adherence to exclusion and inclusion criteria during screening. The proposed research will expose the participants to a minor increase over minimal risk. The exclusion criteria include, but are not limited to, contraindications to PHN/TPM. Participant assessments will be done at study visits every three months. Participants and their parent/guardian (if < 18 years) will be provided with contact information for [name] (study PI), clinical nurse, and the research coordinator with explicit instructions to contact the study team in the event of emergencies.

**Participant Stopping Rules:** In the event that a participant has a serious adverse event that is deemed related to the study medication and/or procedures by the PI, the participant will be required to immediately discontinue the intervention. The overall study may be stopped at any time at the request of the PI and/or the DSMB. Participants will be removed from the study if suicidal ideation, excessive

weight loss, or disordered eating is present at any time during the trial or if any clinically significant changes (at the discretion of the PI) in mood and/or depression are observed. If the ratio of participants on medication vs. placebo developing a serious adverse event requiring withdrawal exceeds 4:1 (after  $\geq 50\%$  enrollment and a minimum of 5 total events, regardless of group assignment), the trial will be stopped. Patients will be instructed that they may withdraw from the study at any time and for any reason without impact on their typical clinical care.

**Study Integrity:** As stated above, the study will undergo annual monitoring of the facility, staff, and study documents by clinical research associates of the University of Minnesota Clinical Trials Monitoring Service. Monitoring staff will provide a summary report to [name] and her mentorship team after each site visit. If necessary, corrective action plans will be devised and implemented by [name] to address deficiencies.

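### Section 17.2 removes a participant for any suicidal ideation, but 5.2 requires no referral when the ideation is below C-SSRS type 4, PHQ-9 is under 10 and there is no suicidal behavior

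*Combined protocol and SAP*

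**What the plan says.** **Removal (17.2, Participant Stopping Rules).** "Participants will be removed from the study if suicidal ideation, excessive" and, completing the list, "weight loss, or disordered eating is present at any time during the trial". Nothing in the sentence grades ideation by intent. The PI's discretion attaches only to the later clause on changes in mood or depression. Suicidal behavior is not named in this sentence.

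**Confirmation and weaning (12.1, Foreseeable Risks).** When a questionnaire shows suicidal behavior, or ideation with some intent, "then test results will be confirmed by the PI prior to discharging the subject from the study". At the same threshold, "Study medications will be weaned off if there is suicidal behavior or ideation with some intent to act on it".

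**Referral (5.2, Study Procedures).** For the PHQ-9: "A participant will be referred to a mental health professional or primary care provider if s/he has a PHQ-9 score of" 10 or more, or on report of suicidal behavior. For the C-SSRS the trigger is "any suicidal behavior or any suicidal ideation of type 4 or 5 on the C-SSRS". Section 8.2 labels Question 4 as active ideation with some intent but no specific plan, so the C-SSRS referral threshold and the 12.1 threshold fall at the same point on the scale.

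**Purpose of the questionnaires (12.1).** They are justified because the chance to "provide an intervention if an individual develops unhealthy eating habits or suicidal ideations is felt to outweigh the risks". No intent threshold is attached there either.

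**The concern.** Participants are 12 to 20 years old, and 12.1 itself says that topiramate can raise the risk of suicidal ideation and behavior. The plan treats ideation of any grade as serious enough to end participation, yet it makes referral compulsory only at a higher grade. Followed exactly, it can take an adolescent with newly reported ideation out of the study, and so out of its scheduled screening, without requiring that anyone else take over care. The differing thresholds carry a second, smaller risk: staff working from 12.1 alone may not see that 17.2 requires removal at a lower grade. The matter is one of participant safety and not of the primary estimate.

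**Working it through.** No arithmetic applies, and the plan states no figure on this point. The check sets the rules side by side and asks what each one requires.

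**Inputs.** Removal rule from 17.2; confirmation and wean rule from 12.1; referral triggers from 5.2; meaning of C-SSRS Question 4 from 8.2; withdrawal provisions from 11.1 to 11.3; adverse event follow-up from 12.7; taper from 4.1 and 8.3.

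**Required actions by presentation.**

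| On-study finding | Removal or discharge | 12.1 confirmation and wean | Referral under 5.2 |
|---|---|---|---|
| Ideation below type 4, PHQ-9 under 10, no behavior | Yes (17.2) | Not triggered | **Not required** |
| Ideation below type 4, PHQ-9 10 or more, no behavior | Yes (17.2) | Not triggered | Yes (PHQ-9 score) |
| Ideation of type 4 or 5 | Yes (17.2) | Yes | Yes (C-SSRS) |
| Suicidal behavior, with or without ideation | Yes (12.1; also 17.2 if ideation is present) | Yes | Yes (both instruments) |

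The rows show which combinations the text covers. They say nothing about how often each occurs, and the split into rows is a choice, so no ratio should be read from them.

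**Do the rules conflict?** No. Everyone who reaches the 12.1 threshold through ideation also meets 17.2. Removing a participant under 17.2 breaches nothing in 12.1.

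**Does another section close the gap in the first row?**

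- Section 11.1 allows a final visit, if the PI thinks it necessary, for participants who ask to withdraw. It covers a physical examination, A1c and insulin adjustment, with no mental health assessment or referral.
- Section 11.2 offers continued visits off drug to those who wish to withdraw. It does not address those removed for safety.
- Section 12.7 has adverse events followed until they resolve or stabilize. New or worsened ideation would fall under that duty. It obliges the study to track the outcome and does not oblige it to refer.

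None of these requires a referral, so the gap in the first row stands.

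**The case against.** The strongest reply is that this is a deliberate graded scheme: a broad stopping rule, with extra steps as severity rises. Section 8.2 is built in a similar way, with one exclusion turning on Questions 4 and 5 and another on any ideation in the previous 30 days. Removal is itself a response, the screening rationale in 12.1 speaks of intervention and not of referral, and nothing stops the PI from referring below the compulsory trigger. Much of this is fair. It shows that the rules are compatible. It does not explain why ideation serious enough for mandatory removal should leave referral to discretion.

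A reader might go further in four ways that the documents do not support.

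- **That 12.1 and 17.2 contradict each other.** They nest, as shown above.
- **That participants removed early have no taper.** Section 4.1 gives a seven-day alternate-day taper to all participants after the final study visit and names no week, and 11.1 uses the same term for an early-withdrawal visit. Section 8.3 places the taper instructions at week 52, so coverage of early removals is unclear, but absence cannot be asserted. Nor do the documents settle whether tapering beats stopping at once in someone removed for ideation. After a related serious adverse event, 17.2 says "the participant will be required to immediately discontinue the intervention".
- **That follow-up of the ideation ends after seven days.** The seven-day limit in 12.7 concerns the start dates of new non-serious events, not follow-up of an event already recorded.
- **That the gap's frequency can be judged from visit schedules or entry criteria.** Counts of scheduled screens do not measure incidence, and a 30-day exclusion at entry does not bound what happens over 52 weeks.

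**Conclusion.** The point holds in a limited form and should be fixed. The removal threshold in 17.2 is lower than the referral threshold in 5.2, and a participant with ideation below type 4, PHQ-9 under 10 and no suicidal behavior falls between them: removal is mandatory and referral is not. The thresholds in 12.1 and 17.2 also differ without explanation, although they are compatible.

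This rests on reading the 17.2 wording as it stands, with ideation unqualified, and on the current text of the sections named. Consent text was not available and could not be checked.

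No incidence is claimed, because the documents give none. The effect on the primary analysis should be small: removed participants remain in the intention-to-treat comparison (14.1, 14.3), and 14.4 carries the last observation forward where the final measurement is missing. A reader might infer a threat to the trial's main result; the text does not support that.

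**What to change.** 1. In 5.2, require referral for any on-study suicidal ideation or suicidal behavior, and keep the PHQ-9 trigger at 10 or more.
2. In 12.1, state the same removal trigger as 17.2: any suicidal ideation, plus suicidal behavior. Name behavior in the 17.2 sentence as well, so that the two sections read alike.
3. Optionally, say in 4.1 or 17.2 whether the taper applies to early removals, leaving the choice between taper and immediate stop to the PI, subject to the 17.2 rule for related serious adverse events.

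The cost is a wording amendment to these sections and a check that the consent text agrees. The downside is a few extra referrals, at most one per removed participant, since each can be removed only once. No visits or tests are added.
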